16.0 Health Information and Privacy Compliance

16.1 **Select which of the following is applicable to your research:**

My research does not require access to individual health information and therefore assert HIPAA does not apply.

I am requesting that all research participants sign a HIPCO approved HIPAA Disclosure Authorization to participate in the research (either the standalone form or the combined consent and HIPAA Authorization).

I am requesting the IRB to approve a Waiver or an alteration of research participant authorization to participate in the research.

An external IRB (e.g. Advarra) is reviewing and we are requesting use of the authorization language embedded in the template consent form in lieu of the U of M stand-alone HIPAA Authorization. Note: External IRB must be serving as the privacy board for this option.

16.2 **Identify the source of Private Health Information you will be using for your research (Check all that apply)**

MEDICAL PROTOCOL (HRP-590)

SHORT PROTOCOL TITLE: Randomized control trial of losartan for outpatients with COVID-19

VERSION DATE:5APR2020

- I will use the Informatics Consulting Services (ICS) available through CTSI (also referred to as the University's Information Exchange (IE) or data shelter) to pull records for me
- I will collect information directly from research participants.
- I will use University services to access and retrieve records from the Bone Marrow Transplant (BMPT) database, also known as the HSCT (Hematopoietic Stem Cell Transplant) database.
- I will pull records directly from EPIC.
- I will retrieve record directly from axiUm / MiPACS
- I will receive data from the Center for Medicare/Medicaid Services
- I will receive a limited data set from another institution
- Other. Describe: CTSI's BPIC will be used to pull structured data directly from EPIC into redcap (ED vitals, labs, etc.). HCMC will enter data into our Redcap research database. Study coordinators will contact patients daily to obtain data and will input it directly into the Redcap research database.

16.3 *Explain how you will ensure that only records of patients who have agreed to have their information used for research will be reviewed:* Study coordinators and BPIC will review if patients have opted out of research by using the opt-out flag within Epic to determine research status. Only patients that have opted-in to research or have expressed that they wish to delay opt-out status will be included in this study.

16.4 *Approximate number of records required for review:* 580, BPIC will be used to extract structured data, for unstructured data or patients that are not admitted to the hospital phone calls by study coordinators will collect data which will be manually entered into Redcap.

16.5 *Please describe how you will communicate with research participants during the course of this research. Check all applicable boxes:*

- This research involves record review only. There will be no communication with research participants.
- Communication with research participants will take place in the course of treatment, through MyChart, or other similar forms of communication used with patients receiving treatment.
- Communication with research participants will take place outside of treatment settings. If this box is selected, please describe the type of communication and how it will be received by participants.

16.6 *Explain how the research team has legitimate access to patients/potential participants:* Informed consent will be obtained from patients granting access to clinical data for study participants.

16.7 *Location(s) of storage, sharing and analysis of research data, including any links to research data (check all that apply).*

- In the data shelter of the [Information Exchange \(IE\)](#)

MEDICAL PROTOCOL (HRP-590)

SHORT PROTOCOL TITLE: Randomized control trial of losartan for outpatients with COVID-19

VERSION DATE:5APR2020

Store Analyze Share

In the Bone Marrow Transplant (BMT) database, also known as the HSCT (Hematopoietic Stem Cell Transplant) Database

Store Analyze Share

In REDCap (recap.ahc.umn.edu)

Store Analyze Share

In Qualtrics (qualtrics.umn.edu)

Store Analyze Share

In OnCore (oncore.umn.edu)

Store Analyze Share

In the University's Box Secure Storage (box.umn.edu)

Store Analyze Share

In an AHC-IS supported server. Provide folder path, location of server and IT Support Contact:

Store Analyze Share

In an AHC-IS supported desktop or laptop.

Provide UMN device numbers of all devices:

Store Analyze Share

Other. Describe:

Indicate if data will be collected, downloaded, accessed, shared or stored using a server, desktop, laptop, external drive or mobile device (including a tablet computer such as an iPad or a smart device (iPhone or Android devices) that you have not already identified in the preceding questions

will use a server not previously listed to collect/download research data

will use a desktop or laptop not previously listed

will use an external hard drive or USB drive ("flash" or "thumb" drives) not previously listed

will use a mobile device such as an tablet or smartphone not previously listed

16.8 Consultants. Vendors. Third Parties. N/A

16.9 Links to identifiable data: All information that identifies study subjects will be handled in accordance with regulatory bodies including HIPAA regulations and the cIRB. This information will be made only available to the principal investigators and study personnel who directly participate in the research calls. Prior to enrollment, participants will sign an authorization to use and disclose PHI for research purposes. All staff will have been trained in the use of PHI. Subjects will be assigned a random subject ID number and a link between identifiers will be maintained in an excel log which will be stored in a secure folder in the AHC-IE

data shelter, the University of Minnesota's most secure healthcare research environment. Only the principal investigators and study nurses will have access to this file.

- 16.10 *Sharing of Data with Research Team Members:* A fully de-identified (of all PHI) database will be generated which will be used for statistical analysis and for monitoring by our DSMB. This database will exist within Redcap.
- 16.11 *Storage and Disposal of Paper Documents:* At this time we do not anticipate any paper documents related to this study. Everything, including consents will be done electronically. If the need for paper collection templates becomes evident, these documents will be stored in locked rooms where only study personnel have access. They will be maintained for 7 years as legally required, after which time they will either be destroyed or moved to long-term storage.

17.0 Confidentiality

- 17.1 *Data Security:* All data will be stored on servers (Redcap and CTSI AHC-IE data shelter) managed by the University of Minnesota IS. No data will be stored on individual research computers, flash drives, etc. These servers Redcap and the data shelter meet all data regulatory requirements and are HIPAA compliant.

18.0 Provisions to Monitor the Data to Ensure the Safety of Participants

- 18.1 *Data Integrity Monitoring:* Data entry will be performed by trained members of the research team who have received documented delegation of authority. Data integrity will be overseen by the PIs. A monitor from Clinical Translational Science Institute (CTSI) will review 100% of electronic consent documents, study drug administration data, and SAE reporting. Additionally, a random sampling of 5% of subjects will undergo full evaluation and comparison of source documentation with data entered into the study database. The first data monitoring visit will be scheduled once 10% of the cohort has been enrolled, with repeat monitoring after 50% and 100% of enrollments. Monitors will evaluate 100% of users to ensure assigned access is consistent with training and delegation of authority logs. The project research coordinators at the sites will maintain binders containing pertinent documents and information including IRB approval letters, documentation of GCP training, licenses, human subjects research ethics training certificates, curriculum vitae, and correspondence.

18.2 Adverse events reporting

- *Definition of an Adverse Event (AE):* An AE is any symptom, sign, illness, or experience that develops or worsens in severity during the course of the study but does not necessarily have a causal relationship with study agent/intervention or procedures. A clinical trial adverse event is defined as any untoward medical event associated with the use of a drug or study procedure. The Investigators will determine daily if any adverse events occur during the period from enrollment (signing of the informed consent) through study day 15. Investigators will determine if the event is serious or related to the study drug. The rationale for this time window is the half-life of 2 hours for losartan and 6-9 hours for its metabolite. Even in the setting of impaired clearance, 3 days after study drug cessation is more than adequate to help to define the period at risk from losartan. Abnormal

MEDICAL PROTOCOL (HRP-590)

SHORT PROTOCOL TITLE: Randomized control trial of losartan for outpatients with COVID-19

VERSION DATE:5APR2020

results of diagnostic procedures are considered to be AEs if the abnormality:

- results in study withdrawal,
- is associated with a serious adverse event (SAE),
- leads to additional treatment or to further diagnostic tests, or
- is considered by the Investigator to be of clinical significance.

- **Definition of a Serious Adverse Event:** Adverse events are classified as serious or non-serious. An SAE is any AE that is:

- *Fatal,*
- *life-threatening,*
- *requires or prolongs a hospital stay,*
- *results in persistent or significant disability or incapacity,*
- *a congenital anomaly or birth defect, or*
- *an important medical event.*

Important medical events are those that may not be immediately life threatening, but are clearly of major clinical significance. They may jeopardize the subject, and may require intervention to prevent 1 of the other serious outcomes noted above. For example, drug overdose or abuse, a seizure that did not result in in-patient hospitalization, or intensive treatment of bronchospasm in an emergency department would typically be considered serious. Serious adverse events will be collected during the first 15 study days, regardless of the investigator's opinion of causation. Thereafter, serious adverse events are not required to be reported unless the investigator feels the events were related to either study drug or a protocol procedure.

Study site personnel must alert a study investigator of any serious and study drug or study procedure related adverse event within 24 hours of investigator awareness of the event. Alerts issued via telephone are to be immediately followed with official notification on the adverse event case report form.

All AEs that do not meet any of the criteria for serious should be regarded as non-serious AEs.

- **Preexisting Condition:** A preexisting condition is one that is present at the start of the study. A preexisting condition will be recorded as an AE if the frequency, intensity, or the character of the condition worsens during the study period.
- **Post-study Adverse Event:** All unresolved AEs will be followed by the Investigator until the events are resolved, the subject is lost to follow-up, or the AE is otherwise explained. At the last scheduled visit, study personnel will instruct each subject to report any subsequent event(s) within 3 months of study completion that the subject, or the subject's

MEDICAL PROTOCOL (HRP-590)

SHORT PROTOCOL TITLE: Randomized control trial of losartan for outpatients with COVID-19

VERSION DATE:5APR2020

personal physician, believes might reasonably be related to participation in this study.

- ***Abnormal Laboratory Values:*** A clinical laboratory abnormality should be documented as an AE if any 1 of the following conditions is met:

- The abnormality suggests a disease and/or organ toxicity that worsened from the time of enrollment, or
- The abnormality is of a degree that requires active management; e.g., change of dose, discontinuation of the drug, more frequent follow-up assessments, further diagnostic investigation, etc.

- ***Continuous SAEs of interest monitoring:*** The following SAEs will be continuously reported to the DSMB: deaths, hospitalization, cardiovascular events (need for vasoactive drugs or fluids for hypotension), or respiratory events (worsening hypoxia, worsening acute respiratory distress syndrome, or new respiratory failure).

- ***Other clinical Outcomes that may be exempt from adverse event reporting:*** Study specific outcomes as outlined in 5.1 and 5.2 are exempt from adverse event reporting unless the investigator deems the event to be related to the study procedures (or of uncertain relationship) or if the event leads to discontinuation of study procedures. The following are examples of events that will be considered study specific clinical outcomes and will be systematically tracked through the study design. The rationale for this criteria is that adverse event reporting can be sporadic and inconsistent, so events more likely to be truly related to a study intervention are better treated by consistent tracking through the systemic design and collection of potentially related adverse events:

- Hepatic events: hepatic injury or liver dysfunction that leads to an increase from baseline in the serum level of bilirubin.
- Renal events: renal failure, renal insufficiency, or renal injury that leads to an increase from baseline in serum creatinine.
- Hematologic/coagulation events: coagulopathy, disseminated intravascular coagulation, thrombocytopenia, or thrombocytosis.
- Changes in serum sodium and potassium

- ***Scales Used to Grade Severity of Adverse Events:*** All AEs will be graded in the following manner:

- Grade 1 (Mild): Events require minimal or no treatment and do not interfere with the participant's daily activities.
- Grade 2 (Moderate): Events result in a low level of inconvenience or concern. Moderate events may cause some interference with functioning.
- Grade 3 (Severe): Events interrupt a participant's usual daily activity and may require systemic drug therapy or other treatment. Severe events are usually incapacitating.
- Grade 4 (Life-threatening): Any adverse drug experience that places the participant, in the view of the Investigator, at immediate risk of death from the reaction as it occurred (i.e., it does not include a reaction that had it occurred in a more severe form, might have caused death).
- Grade 5 (Death)

- **Scales Used Attribute Adverse Events:** The Principal Investigator will assess the relationship of all AEs to any drug or study procedure:
 - **Definitely Related:** There is clear evidence to suggest a causal relationship, and other possible contributing factors can be ruled out. The clinical event, including an abnormal laboratory test result, occurs in a plausible time relationship to study agent/intervention administration and cannot be explained by concurrent disease or other drugs or chemicals. The response to withdrawal of the study agent/intervention (de-challenge) should be clinically plausible. The event must be pharmacologically or phenomenologically definitive, with use of a satisfactory re-challenge procedure if necessary.
 - **Probably Related:** There is evidence to suggest a causal relationship, and the influence of other factors is unlikely. The clinical event, including an abnormal laboratory test result, occurs within a reasonable time sequence to administration of the study agent/intervention, is unlikely to be attributed to concurrent disease or other drugs or chemicals, and follows a clinically reasonable response on withdrawal (de-challenge). Re-challenge information is not required to fulfill this definition.
 - **Possibly Related:** There is some evidence to suggest a causal relationship (e.g., the event occurred within a reasonable time after administration of the trial medication). However, the influence of other factors may have contributed to the event (e.g., the subject's clinical condition, other concomitant events). Although an adverse drug event may rate only as "possible" soon after discovery, it can be flagged as requiring more information and later be upgraded to probable or certain as appropriate.
 - **Unlikely:** A clinical event, including an abnormal laboratory test result, whose temporal relationship to study agent/intervention administration makes a causal relationship improbable (e.g., the event did not occur within a reasonable time after administration of the trial medication) and in which other drugs or chemicals or underlying disease provides plausible explanations (e.g., the subject's clinical condition, other concomitant treatments).
 - **Not related:** The AE is completely independent of study agent/intervention administration, and/or evidence exists that the event is definitely related to another etiology. There must be an alternative, definitive etiology documented by the clinician.
- **Anticipated Adverse Events:** Adverse events are not expected from any of the study procedures. We do not expect any serious adverse events due to losartan.
- **Recording and Documentation**
 - At each contact with the subject, personnel must seek information as to discomforts or adverse experiences by specific questioning and, as appropriate, by examination. This will typically occur via phone or telemedicine due to concerns regarding infectious

contagion. Information about AEs to be recorded includes event description, time of onset, investigator assessment of severity, relationship to Study Agent(s)/Intervention(s), and time of resolution/stabilization of the event. All AEs occurring during the study period (from time of consent signing to study day 15) must be documented appropriately regardless of relationship to study products or procedures unless included on the list of clinical outcomes that may be exempt from adverse outcomes reporting as part of the study protocol and outcomes. Information on all identified AEs will be recorded within 5 days recognition, while SAEs will be reported within 24 hours in the appropriate AE module of the case report form (CRF) on Redcap.

18.3 Data Safety Monitoring: A data safety monitoring board (DSMB) has been convened and includes 4 individuals meeting the key element criteria below, and includes a biostatistician with prior clinical trials DSMB experience. The DSMB will follow the guidance as outlined in the application and the attached charter unless there is a compelling, unanticipated reason to deviate from these rules. Data regarding the primary outcome (hospitalization) will be reported to the DSMB continuously, consistent with continuous study monitoring principles. The DSMB may recommend stopping the trial early only for safety, following these guidelines:

[Patient Safety] A recommendation to suspend, alter the study, or stop for harm would occur if during continuous monitoring there is strong evidence that the rate of IRB-reported SAEs was significantly higher in the experimental group than in the placebo group. SAEs (including hospitalization, the primary SAE of interest) will be reported within 24 hours, allowing for continuous study monitoring. We will conduct formal interim analyses for safety at 5%, 10%, 15%, 20%, 30%, and 50% of enrollment. With a baseline event rate of 15%, this corresponds to formal analyses after every ~5 events initially, decreasing to every ~10 as data accumulates. Despite the lower number of formal preplanned analyses, the DSMB will still receive near *real-time reporting of hospitalizations and deaths*, and can deviate from this strategy and perform earlier testing if desired. They retain authority to change this plan if the continuous reporting suggests harm prior to the first formal planned assessment if they feel that a formal hypothesis test is warranted. In addition, the DSMB may request additional safety assessments after the 50% assessment, if they feel that additional formal testing is needed.

The DSMB will operate in accordance with guidelines established by the FDA in "Guidance for Clinical Trial Sponsors: Establishment and Operation of Clinical Trial Data Monitoring Committee" jointly published by the CBER, CDER and CDRH of the FDA (<https://www.fda.gov/regulatory-information/search-fda-guidance-documents/establishment-and-operation-clinical-trial-data-monitoring-committees>). The key elements include:

1. Expertise and independence: The members must have expertise in the area of study, not be study authors and have no financial conflict of interest.
2. Members will sign a confidentiality agreement.
3. It is preferred that the DSMB have a face-to-face initial meeting, but can meet by telephone thereafter more frequently.

4. All meetings must follow standard operating procedures (SOPs).

If the DSMB recommends closure of the study, then the DSMB Chair will email the principal investigator and IRB. If the trial is stopped for patient safety and a repairable cause of unacceptably high adverse events can be identified, the action must be reviewed and approved by the DSMB and IRB prior to resuming enrollment. For example, if one additional exclusion criterion is discovered that would account for the majority of unexpected events, this new exclusion criterion could be added, and the study could proceed.

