1.0 Objectives

- 1.1 *Title:* Randomized Controlled Trial of Losartan for outpatients with COVID-19
- 1.2 *Purpose:* To determine the impact of losartan compared to placebo on the rate of hospitalization in outpatients diagnosed with COVID19 not requiring hospital admission at the time of initial presentation.
- 1.3 *Hypothesis:* Losartan will significantly reduce the rate of hospitalization at 15 days in outpatients not requiring hospitalization after initial presentation.
- 1.4 *Study design:* Multi-center, prospective, randomized blinded interventional trial of losartan (25 mg orally twice daily) versus placebo administered for 10 days or until hospital admission.
- 1.5 *Study procedures:*
 - The trial emphasizes early intervention to prevent the progression of respiratory disease. Patients presenting to the emergency department or outpatient drive-thru COVID-19 clinics who test positive for the virus will be eligible for enrollment and randomization within 72 hours of test result and no more than 7 days from symptom onset.
 - Investigators and research coordinators will leverage already functional electronic consent procedures to enroll patients safely while also minimizing risk to study staff. Patients tested at all locations will be given a brochure with study information instructing them to contact the study team if interested in a clinical trial (see attached patient-facing study related materials). In addition, patients receiving test results by phone from the clinical care team will be alerted they may qualify for a research study and that study team members may contact the patient about eligibility. The patient may opt-out of such followup calls. The eConsent platform is currently used in NIH supported StrokeNet and SIREN clinical trials, and are HIPAA compliant.
 - Enrolled patients will be randomized to losartan or placebo, and undergo daily assessment by study personnel with built-in safety and efficacy assessments. Enrolled participants will be delivered study drug, a thermometer, oropharyngeal swabs, home blood pressure cuff, and a urine pregnancy test, if applicable, by courier service within 24 hours of randomization. Study personnel will call patients every other day during the intervention window to review study drug adherence, review symptoms for possible adverse events, remind patients to collect oropharyngeal swabs, and administer validated outpatient dyspnea assessments at predetermined time points.

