4.0 Study Interventions / Interventional Agents

4.1 *Intervention arm:* The intervention is losartan, an angiotensin receptor blocker, in microcrystalline methylcellulose, administered at 25 mg PO twice daily for 10 days (patients with eGFR 30-60 mL/min/1.73 m² will be given 25 mg once daily) or until hospital admission, whichever comes first.

- *Rationale for the duration of the intervention:* The average time from symptom onset to hospitalization based on reports to date is 8-9 days.^{7,31} We expect participants to present with at least 1-2 days of symptoms. We expect most participants to reach their primary endpoint within 10 days of treatment (11-12 days from symptom onset), which represents our time of maximal efficacy of the intervention in this cohort. We have chosen to stop treatment at the time of hospitalization as the participant may or may not be admitted to a participating hospital, introducing significant logistical limitations.
- *Rationale for the dose of treatment:* The lowest dose of losartan is 25 mg orally, which minimize risk of side effects and AEs to the patient. The maximum clinical dose is 100 mg daily. Losartan has a half-life of 2 hours with an active metabolite E3174 of 6-9 hours. The threshold for blockade of angiotensin-II receptor is at least 20 mg per day.³² Twice daily dosing has been shown to potentiate angiotensin-II receptor blockade compared with once daily dosing. We propose a dose of 25mg twice daily. At this dose, extrapolated data suggest 37% inhibition of angiotensin-II receptors, which we believe represents an excellent risk: benefit ratio for trial participants. At the highest maximum allowable clinical dose (50 mg twice daily) we would anticipate 50% inhibition of angiotensin-II receptor.³² Multiple early pharmacokinetic studies of losartan at the low-dose demonstrates the drug has minimal side effects on blood pressure (consistently <10 mmHg reduction in maximal systolic blood pressure) in healthy patients³³⁻³⁶ without an overactive renin-angiotensin-aldosterone system. Clinical exclusion criteria has been added to identify patients who might be at increased risk for side effects. Patients with moderate renal dysfunction (eGFR 30-60 mL/min/1.73 m² will be given 25 mg once daily given impaired renal clearance.

4.2 *Placebo arm.* Placebo capsules will match, and contain microcrystalline methylcellulose only.

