5.4 *Patient follow-up:* Participants will receive phone calls by trained study personnel every other day for the 10 days of the intervention period to monitor for the development of complications including lowest daily blood pressure (measured at least once by home blood pressure cuff provided to the patient and medication compliance. Data will be documented into a Redcap database. The coordinators will have participants complete 2 qualitative surveys at enrollment, day 4, and day 10 (both attached in supplement). Surveys and adverse event assessments conducted within 1 day of the time point will be counted as qualifying and not considered missing. At day 15 (+/- 2 day), patients will be asked to return for repeat research blood draw to include creatinine testing. Patients will be contacted by phone at day 28 (+/- 3 days) and 90 (+/- 3 days) for short and intermediate term outcomes. If there is no follow-up due to lack of patient response, this will be documented and not counted as a protocol deviation.

MEDICAL PROTOCOL (HRP-590)

SHORT PROTOCOL TITLE: Randomized control trial of losartan for outpatients with COVID-19

VERSION DATE:5APR2020

5.5 *Table of events:*

		Study Day																			
	Screening / Enrollment ^{t*}	1	2	3	4	5	6	7	8	9	10	11	12	13	14	15	28	90			
ELIGIBILITY																					
Covid-19 Result confirmation	X																				
Inclusion / Exclusion	X																				
Informed Consent	X																				
ADDITIONAL POST-ENROLLMENT PRESCREENING (IF NOT ALREADY AVAILABLE)																					
Pregnancy assessment and birth control X plan**	X																				
Blood Pressure within 1 week of randomization	X																				
Creatinine / Potassium within 1 week of randomization	X																				
Randomize subject if eligible after additional prescreening	X																				
POST-RANDOMIZATION																					
Demographics	X																				
Medical History / CRF	X																				
Dispense / administer study drug**	X	X	X	X	X	X	X	X	X	X	X										
STUDY PROCEDURES (while outpatient) #																					
Assessment of Hospitalization			X		X		X		X		X								X	X	
Adverse event assessment			X		X		X		X		X								X	X	
Review adherence			X		X		X		X		X										
Review and record blood pressures and temperatures			X		X		X		X		X										
PROMIS Survey					X							X							X		

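### Daily AE determination through day 15 is stated, but calls are every other day for 10 days, and participants who skip the day-15 draw or attend it early have no scheduled contact covering the end of the window until day 28

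*Combined protocol and SAP*

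**What the plan says.** **Daily.** Section 18.2: "The Investigators will determine daily if any adverse events occur during the period from enrollment", a period it runs from consent through study day 15. Section 1.5 says enrolled patients will "undergo daily assessment by study personnel with built-in safety and efficacy assessments". Section 16.2 adds: "Study coordinators will contact patients daily to obtain data".

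**Every other day.** Section 5.4: "Participants will receive phone calls by trained study personnel every other day for the 10 days of the intervention period". Sections 1.5 and 1.6 also describe every-other-day contact, so 1.5 says both.

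**After the intervention period.** Section 5.4 asks patients to return for a research blood draw at day 15 (±2 days) and schedules calls at day 28 (±3) and day 90 (±3). Lack of patient response is documented but is not a deviation. Section 6.2 likewise exempts missed biospecimens other than the baseline laboratory tests.

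**Windows.** The primary endpoint is hospital admission at 15 days from randomization (3.1). For safety, "Serious adverse events will be collected during the first 15 study days, regardless of the investigator's opinion of causation" (18.2).

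**How events become known.** Section 18.2 requires specific questioning about AEs at each contact. Section 1.6 determines final outcomes from patient report, record review and the death index. Section 4.1 accepts that "the participant may or may not be admitted to a participating hospital", and for outside admissions 1.6 relies on contacting the patient for permission to request data.

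**Reporting.** One rule in 18.2 requires serious, study-related events to be alerted within 24 hours of investigator awareness. The case-report-form rule in 18.2 and the DSMB text in 18.3 also say 24 hours but do not say when the clock starts. Section 18.3 relies on this for near real-time reporting of hospitalizations and deaths.

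**The concern.** The plan states two contact frequencies, and only the sparser one has a schedule behind it. The scheduled calls cover the treatment period, while the AE/SAE window and the primary endpoint both run five days further. The days just after the last dose matter by the plan's own reasoning: 18.2 justifies its window by the period at risk of 3 days after drug cessation, which is days 11-13 for a course ending on day 10.

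At stake is how current the safety information is. Section 13.1 offers continuous DSMB monitoring of the primary outcome as the safeguard against a theorized cardiac risk. The DSMB cannot be told of an admission before the site knows of it. Non-serious AEs first asked about at day 28 would also have onset and resolution recalled from about two weeks earlier.

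**Working it through.** There is no stated figure to reproduce; the check is a count of days. It assumes that study day and days from randomization coincide.

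**Inputs.** Calls on days 2, 4, 6, 8 and 10 (table 5.5, matching 5.4), each ±1 day (table footnote). Draw on days 13-17 (15 ± 2). Next call on days 25-31 (28 ± 3). Window: days 1-15.

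**1. Daily versus scheduled, during treatment.** Calls fall on 5 of the 15 window days, so 10/15 = 67% of days have no call. The nominal gap between calls is 2 days; with the ±1 allowance at both ends it can reach 2 + 1 + 1 = 4 days.

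**2. After the day-10 call.** What is covered depends on whether and when the draw is attended. Delay is the day of next contact minus the day of the event.

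| Day-15 draw | Window days with no later contact until day 28 | Share of 15 days | Delay to the day-28 call, at 28 ± 3 |
|---|---|---|---|
| Skipped | 11-15 | 5/15 = 33% | Day-11 event: 25 − 11 = 14 to 31 − 11 = 20 days; day-15 event: 25 − 15 = 10 to 31 − 15 = 16 days |
| Attended day 13 | 14-15 | 2/15 = 13% | 25 − 15 = 10 to 31 − 14 = 17 days |
| Attended day 14 | 15 | 1/15 = 7% | 25 − 15 = 10 to 31 − 15 = 16 days |
| Attended days 15-17 | none | 0 | Not applicable; a day-11 event is found at the visit, 4 to 6 days later |

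If the last call is made on day 9 or day 11 instead of day 10, the skipped-draw row becomes 6/15 = 40% or 4/15 = 27%.

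**3. Does table 5.5 settle it?** No. The AE and hospitalization rows carry marks on days 2, 4, 6, 8 and 10 and then two more, although three later time points follow (15, 28, 90). The columns are broken in the available text. The first of the two later marks lies in the same extracted column as the potassium/creatinine check, which 5.4 places at day 15. A day-15 assessment can be neither confirmed nor excluded. If one is intended, the table's ±1 allowance would still accept day 14, before the window closes.

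**4. How many participants?** This cannot be computed. The documents do not give the proportion who will miss the draw or attend early, the proportion of admissions on days 11-15, or the proportion at non-participating hospitals.

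**The case against.** The strongest reply is that this is a wording inconsistency with several backstops already in place.

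- An attended day-15 visit is a contact, so 18.2 already requires AE questions there, and section 11.4 offers a $25 gift card for attending. This stands for those who attend on or after day 15. It does not help those who skip the visit, and only partly helps those who come on day 13 or 14.
- Table 5.5 may already mark a day-15 assessment. This stands as a possibility; section 5.4 should then say so.
- Record review, the death index and the day-28 and day-90 calls will pick up most admissions, which are dated and memorable. This stands: detection is late rather than absent. For outside hospitals, though, it rests on patient report.
- The 14-to-20-day delay needs an outside admission, a missed draw and no spontaneous report. This stands; it is a worst case. The consent forms and brochure, which might ask participants to report admissions, are not available here.

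Four stronger readings are tempting and are not supported:

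- *Calls end at day 10.* Only the every-other-day series does; calls follow at days 28 and 90, with a visit between.
- *A third of endpoint events fall in the gap.* The 33% is a share of days for a participant who skips the draw. Applying it to events assumes even timing, whereas 4.1 expects most participants to reach the endpoint within 10 days of treatment.
- *The 24-hour SAE rule is breached.* Where 18.2 states a clock, it starts at awareness. Sparse contact delays awareness; it does not break the rule.
- *The treatment comparison is biased.* Both arms are blinded and share one schedule, and nothing in the documents points to differential ascertainment.

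**Conclusion.** The contradiction is explicit: daily determination through day 15 cannot come from calls on 5 of 15 days. A limited but real gap remains at the end of the window. It affects participants who skip the draw (days 11-15 uncovered) or attend on day 13 or 14 (the last 2 days or 1 day uncovered). For them, an AE or an outside-hospital admission may surface 10 to 20 days after it happens, about two weeks. That falls short of the near real-time DSMB feed in 18.3 and leaves AE details to recall.

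The consequence is mainly lateness, not loss of the primary endpoint. The conclusion rests on 5.4 as written and on non-attendance being permitted; the number of participants affected is unknown. The change should be made, because it is cheap and closes the gap exactly where the safety and endpoint windows end.

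**What to change.** 1. In 5.4, and in 5.5 if it is not already there, specify a contact on or just after day 15. Make it by phone for anyone who did not attend the draw on or after day 15. Ask about hospitalization at any hospital, death, and AEs since the last call.
2. Reconcile 1.5, 16.2 and 18.2 with the contact frequency actually used.
3. State in 18.2 and 18.3 that the 24-hour SAE clock starts at site awareness, so that the DSMB knows how current its feed can be.

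Cost: at most one short call per participant (up to 580) by the existing call team, plus wording changes. Five calls plus one is still well below the 15 daily determinations that 18.2 now states.
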